Trial Objectives	
The overall objective is to assess the safety of ublituximab as add-on therapy to steroids for treatment of acute optic neuritis and/or transverse myelitis in NMO and NMOSD.
 
Primary Objective To assess safety of acute B cell depletion in NMO subjects with acute relapse of optic neuritis and/or transverse myelitis who are treated with ublituximab + steroids beginning on dose administration and ending with repletion of circulating B cells.
 
Secondary Objectives
 
 • To determine the B cell depletion pharmacokinetics of ublituximab in the NMO patient population by monthly B cell counts for up to 9 months. • To determine the frequency of adverse events with ublituximab in this patient population.

	
Clinical secondary efficacy endpoints: Clinical outcomes will be monitored for efficacy using three functional neurologic tests, the Expanded Disability Status Scale (EDSS), Timed 25-Foot Walk and High Contrast Visual Acuity (HCVA). These will be assessed days 1 and 5 of hospitalization, on Days 13 and 20 (if necessary) and at follow up in 90 day and 180 days.
 
Objective secondary efficacy endpoints:
 
 • MRI lesion size • Number of days in hospital • Requirement for plasma exchange rescue therapy 
Pharmacokinetics and Immunogenicity
 
 • To determine the pharmacokinetics of ublituximab in NMO patients • To assess for the effect of immunogenicity on the pharmacokinetics, pharmacodynamics, and safety of ublituximab. 																																																						
Safety Endpoints	All AEs will be reported and evaluated during the treatment period using CTCAE v4.0.																																																						

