	
subjects treated at Johns Hopkins, approximately 50% of NMO/NMOSD subjects improve from a relapse with steroids alone. The other 50% require escalated care with plasma exchange.
 
Plasma Exchange Treatment Phase
 
Should subjects not meet above clinical criteria to be discharged home, escalation to treatment with plasma exchange is standard of care.
 
The plasma exchange treatment phase begins at the end of the Steroid Treatment Phase and will last up to 14 days. During the Plasma Exchange Treatment Phase, subjects will undergo 1.0 – 1.5 volumes of plasma exchange every other day according to standard of care. At the end of this phase, a second MRI may be performed to compare to admitting MRI. If any further acute immunosuppressive treatment for the acute NMO flare is required and provided according to standard of care, the subject will continue to be followed for safety issues, but the clinical efficacy data will not be included in the statistical analysis. Historically among NMO/NMOSD patients treated at the Johns Hopkins Hospital, approximately 95% of NMO/NMOSD patients who complete plasma exchange are discharged following completion of the plasma exchange.
 
Follow-up
 
Every month after discharge, subjects will be followed with monthly B cell counts until their B cell counts replete to a minimum of 0.5% for patients who will continue to be treated with B-cell depleting agents for preventive care, according to standard of care, or to a minimum of 5% for patients who will use other preventive strategies. In addition, complete blood counts with differential to track neutrophil counts and complete metabolic profiles will be completed monthly as well.
 
The secondary efficacy outcome is neurologic function at follow up 90 days and 6 months after initial hospitalization for the acute relapse. In addition to a thorough history and physical examination, including EDSS rating, visual examination and timed walk, a research MRI of the spine will be performed at day 90 to compare to the relapse lesion.

Trial visits	Screening (Day 0), Steroid Treatment Phase (Days 1 to 5), Plasma Exchange Treatment Phase, if necessary (Days 6 to 20), and Follow-up (monthly blood tests and visits on Days 90 and 180).

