5.4 DURATION OF FOLLOW UP

After discharge from the hospital, subjects will be followed as an outpatient clinically at days 90 and 180. In addition, subjects will be monitored monthly for B cell counts for as long as it takes for B cells to replete to a minimum of 0.5% for patients who will continue to be treated with B-cell depleting agents for preventive care, according to standard of care, or to a minimum of 5% for patients who will use other preventive strategies. For most subjects, the duration of B-cell depletion with UTX is up to 9 months. Subjects removed from the trial for unacceptable adverse event(s) will be followed until resolution or stabilization of the adverse event. In addition, subjects will be checked by complete blood count with differential and complete metabolic profile for evidence of toxicity to other cells (e.g., neutrophils) or organs such as kidney or liver function.

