4. An improvement in visual acuity using bedside Snellen chart of ≥ 2 lines.

If subjects do not require escalation to plasma exchange because they fulfill the clinical criteria above, an MRI may be performed to confirm resolution of the inflammatory lesion, according to standard of care at Johns Hopkins. Based on the MRI and other clinical factors, the treating physician may proceed to discharge the subject home or change the plan to escalate immunosuppression to plasma exchange for continued treatment of the acute exacerbation.

Findings by MRI that may influence escalation to plasma exchange typically include extension of enhancement, involvement of new areas of the nervous system or an increase in the area of T2 hyperintensity. Historically among the NMO/NMOSD subjects treated at Johns Hopkins, approximately 50% of NMO/NMOSD subjects improve from a relapse with steroids alone. The other 50% require escalated care with plasma exchange.

Before discharge from the hospital, the subject will be scheduled for follow up in the NMO Clinic in 90 and 180 day visits. In addition, subjects will be sent to a local lab for monthly CD19 monitoring until the B cell counts replete to a minimum of 0.5% for patients who will continue to be treated with B-cell depleting agents for preventive care, according to standard of care, or to a minimum of 5% for patients who will use other preventive strategies. These results will be reviewed by the PI, [name].

Plasma Exchange Treatment Phase

Should subjects not meet above clinical criteria to be discharged home, escalation to treatment with plasma exchange is standard of care.

The plasma exchange treatment phase begins at the end of the Steroid Treatment Phase and will last up to 14 days. During the Plasma Exchange Treatment Phase, subjects will undergo 1.0 – 1.5 volumes of plasma exchange every other day according to standard of care. At the end of this phase, a second MRI may be performed to confirm resolution of the lesion, according to standard of care. If any further acute immunosuppressive treatment for the acute NMO flare is required and provided according to standard of care, the subject will continue to be followed for safety issues, but the clinical efficacy data will not be included in the statistical analysis. Historically among NMO/NMOSD

subjects treated at the Johns Hopkins Hospital, approximately 95% of NMO/NMOSD subjects who complete plasma exchange are discharged following completion of the plasma exchange.

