11.1 SAMPLE SIZE

Hypothesis

This trial is exploring the safety of ublituximab in the treatment of NMO/NMOSD relapses. The hypothesis is that the ublituximab regimen proposed in this trial is safe and tolerable in the NMO/NMOSD patient population. The objectives of the trial will be assessed through the use of summary statistics.

Sample Size Considerations

The sample size of 5 subjects is based on feasibility and logistical considerations on the number of subjects that will reveal a significant risk or tolerability issue of using ublituximab + steroids. It is anticipated that 1 subject will fail screening and 1 will drop out over the course of the trial, for a total of 4 subjects who are expected to complete the trial. Subjects who withdraw will not be replaced.

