11.2 GENERAL ANALYSIS CONVENTION

Interim Analysis

There will be no interim analysis.

Statistical Analysis

A summary of the number and percentage of subjects with any adverse event, any serious adverse event, adverse events leading to permanent discontinuation of trial drug, and trial drug-related adverse events will be reported.

Change in neurologic outcomes on the EDSS, Timed 25-Foot Walk and HCVA scales from admission to discharge will be analyzed by paired t-tests with significant p-values considered less than 0.05.

By MRI, length of T2 hyperintensity and length of T1-post contrast enhancement should be stable or reduced by discharge. A paired t-test will be used to compare changes in these values with significance considered at p-values less than 0.05.

Continuous data will be described using the following descriptive statistics: n, mean, median, minimum and maximum. Data will be displayed in all listings sorted by subject number.

When count data are presented, the percentage will be suppressed when the count is zero in order to draw attention to the non-zero counts. A row denoted "Missing" will be included in count tabulations where necessary to account for dropouts and missing values. Unless otherwise specified, the denominator for percentages will be the number of subjects with a non-missing assessment within the analysis population of interest.

SAS Version 9.2 will be used to perform all analyses.

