12.6.2 Abnormal Laboratory Values and Vital Signs

The reporting of abnormalities of vital signs as adverse events should be avoided. Abnormalities of vital signs should not be reported unless any criterion for an SAE is fulfilled, the vital signs abnormalities cause the subject to discontinue trial treatment, or the investigator insists that the abnormality should be reported as an AE. Any grade 3 or 4 laboratory abnormality or any clinically significant grade 1 or 2 hematology or biochemistry laboratory value(s) should be recorded as an AE. If an abnormal laboratory value or vital sign is associated with clinical signs and/or symptoms, the sign or symptom should be reported as an AE, and the associated laboratory value or vital sign should be considered additional information that must be collected on the relevant CRF.

Clinical Laboratory Results will be summarized. Summary statistics for actual values and for changes from baseline will be tabulated for laboratory results by scheduled visit. Subjects with laboratory values outside of the normal reference range at any post-baseline assessment will be summarized, and graded per NCI CTCAE Version 4.0 when applicable. Subject incidence of laboratory toxicity will be summarized and assigned a maximum grade for each laboratory test.

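### B-cell counts stop at each subject's own repletion, so the by-visit summaries cease to describe the treated group once the first subject stops

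*Combined protocol and SAP*

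**What the plan says.** The synopsis gives as a secondary objective "To determine the B cell depletion pharmacokinetics of ublituximab in the NMO patient population by monthly B cell counts for up to 9 months". Section 2.2 repeats it without the time limit.

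Measurement is tied to the result. Section 5.4 says that "subjects will be monitored monthly for B cell counts for as long as it takes for B cells to replete"; the threshold is 0.5% for patients who will go on with B-cell depleting prevention and 5% for those who will use something else. The synopsis (Follow-up) and section 7 (two places) give the same two-threshold rule. Table S1 and Table 6 list monthly laboratory days from 30 to 270 and do not mention the stop.

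On analysis, section 12.6.2 says: "Summary statistics for actual values and for changes from baseline will be tabulated for laboratory results by scheduled visit". Section 11.2 gives continuous data n, mean, median, minimum and maximum. Unless otherwise specified, it sets the percentage base as follows: "the denominator for percentages will be the number of subjects with a non-missing assessment within the analysis population of interest". The synopsis lists the B-cell count among the laboratory evaluations. No section describes a B-cell-specific analysis, a time to repletion, a censoring rule, or the handling of visits after repletion. Section 11 leaves further data-handling detail to a formal SAP to be finalised before database lock.

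**The concern.** A subject leaves the monthly series because the count has recovered. A summary by visit among those with values therefore drops the earliest to recover first, and the group described changes from visit to visit in a way that depends on the quantity being summarised.

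At stake is the description of how long and how deeply a single infusion depletes B cells in this population. Section 1.4 adds a specific use: plasma exchange may shorten depletion, and the monthly counts are meant to show it. Subjects whose B cells return early are the ones who leave the table first.

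**Working it through.** The plan states no B-cell result and assumes no repletion time, so it has no figure of its own to reproduce. Inputs from the documents are five subjects ("The sample size of 5 subjects is based on feasibility and logistical considerations"), one expected dropout (5 − 1 = 4 completers), monthly visits to Day 270, and the thresholds 0.5% and 5%. Repletion times and speed of recovery below are assumptions.

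**Step 1: direction with one threshold.** Let T be the first monthly visit at which a subject meets the stopping threshold. The subject is measured at visit m only if T ≥ m.

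- Percentage depleted among those measured: #(T > m) / #(T ≥ m)
- Percentage depleted among all five: #(T > m) / 5

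The numerators are equal and the first denominator never exceeds 5. The first percentage is therefore never the lower one. It is strictly higher once one subject has stopped at an earlier visit while another is still below threshold. Subjects who replete at visit m are still measured there.

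**Step 2: one threshold, worked.** Assume 0.5% applies to all and T = 4, 6, 7, 8, 9.

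| Month | Measured | Still below 0.5% | Among measured | Among all five |
|---|---|---|---|---|
| 5 | 4 | 4 | 4/4 = 100% | 4/5 = 80% |
| 6 | 4 | 3 | 3/4 = 75% | 3/5 = 60% |
| 7 | 3 | 2 | 2/3 = 67% | 2/5 = 40% |
| 8 | 2 | 1 | 1/2 = 50% | 1/5 = 20% |

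For the mean, assume 0.1% before repletion, 0.5% at repletion, doubling each month, capped at 8%. At month 8 the mean among those measured is (0.5 + 0.1)/2 = 0.3%. Among all five it is (8 + 2 + 1 + 0.5 + 0.1)/5 = 11.6/5 = 2.3%.

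**Step 3: mixed thresholds.** Keep the same courses but put the month-4 subject on the 5% rule. That subject reads 0.5, 1, 2, 4 and 8% at months 4 to 8, so first reaches 5% at month 8 and is measured up to then.

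- Percentage below 0.5%, measured against all five: month 5, 4/5 and 4/5; month 6, 3/5 and 3/5; month 7, 2/4 = 50% and 2/5 = 40%; month 8, 1/3 = 33% and 1/5 = 20%.
- Mean at month 8: (8 + 0.5 + 0.1)/3 = 2.9% among those measured, against 2.3% in all five.

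The percentage gap vanishes at months 5 and 6 and shrinks afterwards. The mean now errs toward recovery.

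**Step 4: dependence on spread.** In 100,000 simulated trials of five subjects, with a common 5% threshold and normally distributed repletion times of mean 6 months, the percentage depleted among measured against all subjects was:

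- SD 1 month: 31% against 16% at month 7.
- SD 2 months: 61% against 31% at month 7, and 52% against 16% at month 8.

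If all subjects replete at the same visit there is no difference.

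**The case against.** **A by-visit percentage depleted is not a named output.** This stands. The B-cell count is continuous, the sentence in section 11.2 is a general default, and the out-of-range counts in section 12.6.2 are per subject. The percentages above show what such a table would do. The by-visit mean and median are planned, however, and have the same missing values.

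**Nothing is lost from the data.** Largely true. The summaries report n, listings are by subject, and a completer's last monthly draw shows the month of repletion. A row for missing values would reveal the loss, but it would pool repleted subjects with dropouts and correct neither a mean nor a percentage.

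**The later SAP can settle it, and the schedule tables run to Day 270.** The SAP could, but nothing in the present text does. The tables conflict with the explicit stopping rule in the synopsis and in sections 5.4 and 7.

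**The all-subject mean is hypothetical.** This stands. Subjects who stop at 0.5% are those who will continue on a depleting agent, so untreated doubling may never occur. For the same reason, simply drawing everyone to Day 270 is a weak remedy: it could mix the effect of ublituximab with that of the next agent.

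A reader might infer that the plan always exaggerates depletion, that only depleted subjects remain after the first repletion, or that early return after plasma exchange would be hidden. The documents do not support these readings. The two thresholds can turn the mean the other way, subjects repleting at a visit are measured at that visit, and the listings show each course.

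**Conclusion.** The plan as written yields by-visit B-cell summaries whose missing values are caused by the outcome, and it specifies no analysis that avoids this. Under a single threshold, and with counts that do not fall again after recovery, depletion looks deeper and longer than in the treated group. With both thresholds in use, the mean curve can be distorted in either direction.

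The size cannot be fixed from the documents. In the assumed cases the percentage gap runs from none (common repletion visit, or the early visits of the mixed case) to 36 points (52% against 16%). Some spread is plausible, because about half of patients have historically needed plasma exchange and the protocol expects it may shorten depletion.

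The issue is moderate. It concerns a descriptive secondary objective with no test attached, in five subjects whose individual data stay recoverable. It does not call the trial or its safety analysis into question.

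**What to change.** In sections 11.2 and 12.6.2, or in the formal SAP before database lock:

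1. Make the main B-cell summary the per-subject time from infusion to repletion. List the last draw below and the first draw at or above the threshold, by plasma exchange status. Censor at the last draw or at the start of another B-cell depleting agent, whichever comes first. A Kaplan-Meier curve is optional with five subjects.
2. Report time to 0.5% for all subjects, and time to 5% separately for those followed to 5%.
3. If a by-visit percentage is shown, keep subjects already repleted in the denominator as repleted, and show dropouts separately.
4. Do not present by-visit means after the first subject stops as the depletion curve.
5. Reconcile the Day 30 to 270 columns of Tables S1 and 6 with the stop-at-repletion text.

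The cost is wording, with no added blood draws. One data item needs checking: censoring requires the start date of any later depleting agent, and Table 6 does not clearly mark concomitant medication at the follow-up visits.

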11.3 ANALYSIS POPULATIONS

The Intent-to-Treat (ITT) population will be used for the official analysis.

The Safety Population will include all subjects who received one dose of trial drug (UTX). All safety assessments including toxicity will be performed on the Safety Population.

The Per-Protocol Population (PP) will consist of all ITT subjects without a major protocol deviation or protocol violation. The criteria for a major protocol deviation or violation will be determined and documented prior to data base lock. Subject exclusion from the PP population will also be determined and documented prior to database lock. Supportive analyses may be performed based on the PP population.

11.4 SUBJECT DISPOSITION

The disposition of subjects includes the number and percentage of subjects for the following categories: subjects treated (safety population), subjects in the ITT population, subjects completed, and subjects discontinued from the trial. All percentages will be based on the number of subjects enrolled. The reasons for trial discontinuation will also be summarized in this table. Only one reason for trial discontinuation will be recorded. However, all reasons will be presented in the listing.

A listing will present data concerning subject disposition.

11.5 SUBJECT DEMOGRAPHICS AND BASELINE CHARACTERISTICS

Baseline demographic and clinical characteristics will be summarized as percentages for categorical variables and as mean, standard deviation, median, minimum and maximum for continuous measures. The analyses of baseline characteristics will be performed for the ITT Population.

11.6 PRIOR AND CONCOMITANT MEDICATIONS

Prior and concomitant medications will be summarized for the Safety population by World Health Organization (WHO) and MedDRA dictionary. Subjects may have more than one medication per drug class and preferred term. At each level of summarization, a subject is counted once if he/she reported one or more medications at that level.

Prior medications are defined as medications with a stop date occurring before the date of receiving first trial treatment. Concomitant medications are defined as medications with start dates occurring on or after date of receiving first trial treatment. Medications with start and stop dates which bracket the date of first dose will be summarized as both prior and concomitant medications.

11.7 MEDICAL HISTORY

Medical history will be captured at the Screening visit. Medical history will be coded using MedDRA and will be summarized by MedDRA system organ class and preferred term for the Safety population.

11.8 EXTENT OF EXPOSURE

The dose (mg) of trial drug administered (UTX), and the duration of treatment will be summarized with descriptive statistics. The proportion of subjects completing the infusion of trial drug (UTX) will be summarized.

11.9 EFFICACY ANALYSES

Secondary endpoints of clinical outcomes will be monitored for efficacy using three functional neurologic tests, the Expanded Disability Status Scale (EDSS), Timed 25-Foot Walk and High Contrast Visual Acuity (HCVA). These will be assessed days 1 and 5 of hospitalization and weekly thereafter for the first three weeks (Days 13 and 20, if needed). The primary analysis will be a change from baseline to Day 90 and the secondary analyses will be a change from baseline to Days 5, 20, and 6 months.

For this secondary efficacy endpoint, the MRIs will be analyzed for two parameters: length of T2 hyperintensity in the spinal cord and optic nerve and length of T1 post-contrast enhancement if available. The secondary analyses for MRI will be a change from baseline to discharge on Day 5 or 20, as well as a change from baseline to follow up at day 90.

Number of days in the hospital and requirement for plasma exchange will be assessed using descriptive statistics.

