1.4 USE OF PLASMA EXCHANGE

All subjects who fail to clinically respond by Day 5 in the Steroid Treatment Phase will be recommended for plasma exchange as per standard of care. A beneficial response is generally considered an improvement in the specific deficit(s) that led to the hospitalization. Depending on those specific deficits, the criteria that are routinely used at Johns Hopkins to indicate treatment response(s) in motor, sensory, autonomic and visual function are:

1. An improvement in strength by the Motor Research Council strength scale by at least 1 full point in at least two isolated muscles of at least one limb, or
2. An increase of two Rydel tuning fork units in at least one affected limb.
3. Improvement in bowel and/or bladder function from incontinence to at least partial voluntary control.
4. An improvement in visual acuity using bedside Snellen equivalent of ≥ 2 lines.

If subjects do not require escalation to plasma exchange because they fulfill the clinical criteria above, an MRI may be performed to confirm resolution of the inflammatory lesion(s) compared to admission MRI. Based on the MRI and other clinical factors, the treating physician may proceed to discharge the subject home or change the plan to escalate immunosuppression to plasma exchange for continued treatment of the acute exacerbation.

Before discharge from the hospital, the subject will be scheduled for follow up in the NMO Clinic for the 90 and 180 day visits. Findings by MRI that may influence escalation to plasma exchange typically include extension of enhancement, involvement of new areas of the nervous system or an increase in the area of T2 hyperintensity. Historically among the NMO/NMOSD patients treated at Johns Hopkins, approximately 50% of NMO/NMOSD patients improve from a relapse with steroids alone. The other 50% require escalated care with plasma exchange.

Plasma Exchange Treatment Phase

Should subjects not meet above clinical criteria to be discharged home, escalation to treatment with plasma exchange is standard of care.

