3 SUBJECT SELECTION

3.1 ELIGIBILITY CRITERIA

Subjects eligible for enrollment must meet all of the following criteria:

1. Able and willing to provide written informed consent.
2. 18-100 years of age.
3. New acute optic neuritis and/or transverse myelitis. A new clinical event is defined as a clinically significant neurologic deficit(s) on physical exam, not attributable to another disease process, which is different from baseline neurological exam, and attributable to a lesion in the spinal cord, optic nerve or brainstem. New symptoms must be reported within 10 days of onset.
4. Highly suspected or confirmed diagnosis of NMO according to the 2006 revisions of the Wingerchuk diagnostic criteria for NMO (Wingerchuk, 2006), or AQP4 positive NMOSD per the EFNS Guidelines. For NMO, subjects must have two absolute criteria:
 - a. optic neuritis
 - b. myelitis

and at least two of three supportive criteria:

- c. presence of a contiguous spinal cord MRI lesion extending over three or more vertebral segments,
- d. MRI criteria NOT satisfying the revised McDonald diagnostic criteria for MS [Polman, 2011]
- e. NMO-IgG (AQP4) in serum.

For NMOSD, subjects must have longitudinally extensive transverse myelitis (LETM) recurrent isolated optic neuritis (RION)/bilateral optic neuritis (BON), or opticospinal multiple sclerosis (OSMS) that is AQP4 antibody positive

5. The B cell count must be normal (5-20% of total lymphocytes) in subjects who have not received another B cell depleting therapy in the past year. For those on B cell depleting therapy within the past year, a B cell count of at least 0.5% of total lymphocytes is necessary.
6. A female subject is eligible to enter the trial if she is:
 - a. Not pregnant or nursing;
 - b. Of non-childbearing potential (i.e. women who have had a hysterectomy, are post-menopausal, which is defined as >2 years without menses or, in female subjects who have been post-menopausal for <2 years, must be confirmed with Follicle Stimulating Hormone (FSH) and estradiol levels), have both ovaries surgically removed or have current documented tubal ligation)

OR

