18.4 FUNCTIONAL SYSTEM SCORE

The Functional Systems (FS) are scored on a scale of 0 (low level of problems) to 5 (high level of problems) to best reflect the level of disability observed clinically. The “Other” category is not rated numerically, but measures disability related to a particular issue, like motor loss.

In contrast, the total EDSS score is determined by two factors: gait and FS scores. EDSS scores below 4.0 are determined by the FS scores alone. People with EDSS scores of 4.0 and above have some degree of gait impairment. Scores between 4.0 and 9.5 are determined by both gait abilities and the FS scores. For simplicity, many experts gauge the EDSS scores between 4.0 and 9.5 entirely by gait, without considering the FS scores.

Kurtzke Functional Systems Scores (FSS)

Pyramidal Functions

- 0 - Normal
- 1 - Abnormal signs without disability
- 2 - Minimal disability
- 3 - Mild to moderate paraparesis or hemiparesis (detectable weakness but most function sustained for short periods, fatigue a problem); severe monoparesis (almost no function)
- 4 - Marked paraparesis or hemiparesis (function is difficult), moderate quadriplegia (function is decreased but can be sustained for short periods); or monoplegia
- 5 - Paraplegia, hemiplegia, or marked quadriplegia
- 6 - Quadriplegia
- 9 - (Unknown)

Cerebellar Functions

- 0 - Normal
- 1 - Abnormal signs without disability
- 2 - Mild ataxia (tremor or clumsy movements easily seen, minor interference with function)
- 3 - Moderate truncal or limb ataxia (tremor or clumsy movements interfere with function in all spheres)
- 4 - Severe ataxia in all limbs (most function is very difficult)
- 5 - Unable to perform coordinated movements due to ataxia
- 9 - (Unknown)

Record #1 in small box when weakness (grade 3 or worse on pyramidal) interferes with testing.

Brainstem Functions

- 0 - Normal
- 1 - Signs only
- 2 - Moderate nystagmus or other mild disability
- 3 - Severe nystagmus, marked extraocular weakness, or moderate disability of other cranial nerves
- 4 - Marked dysarthria or other marked disability
- 5 - Inability to swallow or speak
- 9 - (Unknown)

Sensory Function

- 0 - Normal
- 1 - Vibration or figure-writing decrease only in one or two limbs
- 2 - Mild decrease in touch or pain or position sense, and/or moderate decrease in vibration in one or two limbs; or vibratory (c/s figure writing) decrease alone in three or four limbs

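### The Timed 25-Foot Walk and HCVA are averaged over all dosed subjects although a relapse may spare walking or vision, so each mean is diluted by subjects with nothing to recover on that scale

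*Combined protocol and SAP*

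**What the plan says.** - **Entry (section 3.1, criterion 3):** "New acute optic neuritis and/or transverse myelitis". A subject may have a visual relapse, a cord relapse or both.
- **Scales (section 11.9):** "Secondary endpoints of clinical outcomes will be monitored for efficacy using three functional neurologic tests". This sentence only names the tests. That the results are pooled follows from the items below.
- **Test (section 11.2):** "Change in neurologic outcomes on the EDSS, Timed 25-Foot Walk and HCVA scales from admission to discharge will be analyzed by paired t-tests". The threshold for significance is set at 0.05. The synopsis extends the same test to Days 90 and 180.
- **Main efficacy time point (section 11.9):** "The primary analysis will be a change from baseline to Day 90". This is the lead analysis of a secondary endpoint, not the trial's primary objective, which is safety.
- **Population (sections 10.1 and 11.3):** the official analysis uses the ITT set, defined as every subject who received a dose. The one stated efficacy exclusion is further acute immunosuppression after plasma exchange (synopsis, sections 1.4 and 7). It has nothing to do with relapse site.
- **Summaries (section 11.2):** "Continuous data will be described using the following descriptive statistics: n, mean, median, minimum and maximum", together with listings by subject number.
- **What the scales measure (section 10):** the walk is described as a test of the legs, and HCVA is a letter-chart score. HCVA is to be tested one eye at a time, yet the score described for recording is binocular, with a maximum of 60 letters.

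No section limits a scale to subjects whose relapse affected that function, or splits results by relapse site.

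**The concern.** A subject admitted with optic neuritis alone has no new walking deficit to regain, and a subject admitted with myelitis alone has no new loss of acuity. Both still enter the mean and the t-test on both scales, each contributing a change near zero. The mean then mixes the size of recovery with the case mix, and the case mix also inflates the standard deviation. With four or five subjects, one or two spared subjects can decide the result. At stake is whether the walk and HCVA results can be read as preliminary evidence of recovery, which section 2.2 gives as the purpose of following them.

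**Working it through.** **The plan's own figure.** Section 11.1 sets 5 subjects by feasibility, with no effect size, SD or power, so there is no formula to reproduce. Its count of completers agrees: 5 − 1 dropout = 4, with the expected screening failure counted outside the five. I use n=4 for Day 90 if the dropout comes before then, and n=5 for discharge.

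**Assumptions.** Spared subjects change by exactly zero. Section 1.1 gives some support, since it describes patients as usually stable between attacks. The test is two-sided at 0.05, because the plan does not state sidedness.

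**Dilution of the mean.** Let k of n subjects be affected, with mean change m. The pooled mean is (k/n)m.

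**Ceiling on t.** The pooled SD is smallest when every affected subject changes by the same m. The sum of squares about the pooled mean is then km² − k²m²/n = m²k(n−k)/n. Dividing by n−1 gives the variance, and t = mean/(SD/√n) reduces to

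t_max = √[k(n−1)/(n−k)].

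The size of m cancels, so a larger recovery does not lift the ceiling.

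| n | Affected k | Pooled mean as share of m | t_max | Critical t | Best p |
|---|---|---|---|---|---|
| 4 | 3 | 75% | √(9/1) = 3.00 | 3.18 | 0.058 |
| 4 | 2 | 50% | √(6/2) = 1.73 | 3.18 | 0.18 |
| 5 | 4 | 80% | √(16/1) = 4.00 | 2.78 | 0.016 |
| 5 | 3 | 60% | √(12/2) = 2.45 | 2.78 | 0.07 |
| 5 | 2 | 40% | √(8/3) = 1.63 | 2.78 | 0.18 |

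Example with an assumed gain: changes of 20, 20, 0, 0, 0 letters give mean 8, SD 10.95, t = 8/(10.95/√5) = 1.63 and p=0.18.

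**How likely a mixed group is.** The documents give no split by relapse site. Let q be the share of subjects affected on a scale, assumed to be 0.3 to 0.7 and independent between subjects.

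- At least one spared of 4: 1 − q⁴ = 0.99 down to 0.76.
- At least two spared of 5: 1 − q⁵ − 5q⁴(1−q) = 0.97 down to 0.47.

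**Relaxing the zero-change assumption.** Suppose affected subjects change by 1.5 SD on average, and spared subjects vary around zero with 0.3 to 1.0 times that SD (all assumed). Power was simulated for the pooled test (200,000 runs) and taken from the noncentral t for affected subjects only.

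| n | Affected k | Power, pooled | Power, affected only |
|---|---|---|---|
| 4 | 3 | 0.09–0.22 | 0.32 |
| 4 | 2 | 0.01–0.09 | 0.13 |
| 5 | 4 | 0.38–0.40 | 0.53 |
| 5 | 3 | 0.06–0.18 | 0.32 |
| 5 | 2 | 0.01–0.09 | 0.13 |

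Over assumed effects of 1.0 to 2.0 SD, affected-only power runs from 0.09 (two affected) to 0.755 (four affected). Restriction removes the dilution of the mean but does not give a dependable test.

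**The case against.** **The individual data will be visible.** Listings by subject, with the minimum and maximum, would show a pattern such as 20, 20, 0, 0, 0 at once. This stands: a recovery would not be hidden from someone who reads the listings. The planned mean and p-value would still misdescribe it.

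**The consequence is small.** This is a single-arm safety study. Section 11.1 says its objectives will be assessed by summary statistics, and section 1.4 puts improvement on steroids alone at about half of patients. Neither the pooled nor the restricted mean isolates a drug effect. This stands too, and it sets the severity.

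**Restriction costs subjects.** Two affected subjects leave one degree of freedom and a critical t of 12.7. Dropping the all-subject summary would also hide new worsening in a system that was unaffected at entry. Both stand, which is why the restricted results should be descriptive and the all-subject summary kept.

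**Stronger readings that the documents do not support.**

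- *That EDSS is diluted in the same way.* Section 18.3 includes a visual functional system. Section 18.4 says that functional systems alone set scores below 4.0, and that gait and functional systems together set scores from 4.0 to 9.5. The sentence that "many experts gauge the EDSS scores between 4.0 and 9.5 entirely by gait, without considering the FS scores" remarks on practice elsewhere; nothing adopts it for this trial. An optic neuritis subject can therefore improve on EDSS.
- *That the plan contradicts its own definition of efficacy.* Section 1.4 does say "A beneficial response is generally considered an improvement in the specific deficit(s) that led to the hospitalization", but there it guides the recommendation of plasma exchange and is not an endpoint. Need for plasma exchange is already a separate secondary endpoint.
- *That significance is always out of reach.* With 5 subjects and one spared it is not.

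**Conclusion.** The point holds for the Timed 25-Foot Walk and HCVA, as a minor one. Each measures one function, and the plan tests its mean change in all dosed subjects (less the immunosuppression exclusion) although a relapse may spare that function. If spared subjects do not change, one spared among 4, or two among 5, puts p<0.05 out of reach whatever the recovery. The exact ceiling rests on that zero-change assumption, and the likelihood of a mixed group rests on an assumed share by relapse site.

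For HCVA the binocular score in section 10 may add to the dilution, because the better eye can mask a deficit in the other. For EDSS there is no analysis error. The primary safety objective is unaffected.

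**What to change.** In section 11.9, or in the formal SAP that section 11 promises:

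1. Make the main HCVA summary the subjects with optic neuritis at entry, and the main walk summary the subjects with a cord or gait deficit at entry. Subjects with both enter both. Report descriptive estimates with individual values.
2. Keep the all-subject summaries as supportive, so that worsening in an unaffected system is still seen.
3. Keep EDSS in all subjects. State that it is scored by functional systems plus gait, as section 18.4 describes, and report the affected functional system score alongside.
4. In section 10, reconcile monocular testing with the binocular score so that affected-eye results are recorded.

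Fix the groups from the entry examination before any outcomes are reviewed. The trial is open-label with five subjects, so groups chosen after results are known would be open to challenge, even before database lock.

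The cost is mainly wording, since relapse site is established at screening and the EDSS examination already yields functional system scores. The possible addition is a case report form field for each eye. The downside is two to four subjects per scale, so p-values carry little weight.
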